## 9.8. Quality Control

For the final reporting, this study will use ORD data derived from claims submitted for payment. Although the health insurance claims data represent financial transactions and are not research records, the financial transactions related to the services provided create financial incentives to record them correctly and fully, so the billable medical services represented in the database are likely to be complete. The validity of this claims research database for epidemiologic research (as compared with data abstracted from medical records) has been widely published ([Dore et al., 2011](#); [Eng et al., 2012](#); [Laughlin, 2011](#); [Quam et al., 1993](#)).

The study will be carried out according to Optum Epidemiology's internal standard operating procedures (SOPs) that are consistent with the Guidelines for Good Pharmacoepidemiology Practices (GPP) published by the European Medicines Agency (EMA) and International Society for Pharmacoepidemiology ([European Medicines Agency, 2017](#); [Public Policy Committee, International Society of Pharmacoepidemiology, 2016](#)) as well as the FDA's Best Practices for Conducting and Reporting Pharmacoepidemiologic Safety Studies Using Electronic Healthcare Data ([FDA, 2013](#)).

Programming for this project will be conducted by a primary analyst and reviewed by a separate analyst (validation analyst). Validation of all statistical programs and results consists of a combination of visual checks (i.e., examination of the programming log, visual printouts before and after data management steps, etc.) and computational checks (i.e., repeating calculations for comparison purposes) performed by a validation analyst. In addition, an epidemiologist and a senior scientist will perform a substantive review of all study deliverables. All validation and quality control procedures are conducted in accordance with Optum SOPs, which prescribe that processes and deliverables are documented, reviewed, and validated in sufficient detail to allow for subsequent re-examination or replication.

## 9.9. Limitations of the Research Methods

The proposed project is based on analysis of automated medical and prescription claims, including pre-adjudicated (interim reporting) and fully adjudicated claims (final reporting).

For the interim report, the SCRI analysis will be based on automated and prospectively collected pre-adjudicated medical and adjudicated prescription claims. A strength of pre-adjudicated medical claims is the shorter lag time between the receipt of care and the appearance of the claim, while the accompanying limitation is that these pre-adjudicated claims may be subject to revision during the adjudication process. A limitation of the SCRI design may be its limited ability to assess chronic outcomes such as MS. Thus, the cohort analysis will be used as the primary analysis for chronic outcomes.

While adjudicated claims data are extremely valuable for the efficient and effective examination of healthcare outcomes, treatment patterns, healthcare resource utilization, and costs, all claims databases have certain inherent limitations because the claims are collected for the purpose of payment, not research. The presence of a diagnosis code on a medical

claim is not confirmation of disease, as the diagnosis code may be incorrectly coded or included as rule-out criteria rather than actual disease.

Another limitation of claims data relates to potential misclassification of exposure covariates. For instance, vaccines that are administered as part of a government program or an office-based or school-based vaccination clinic may not be captured in our database if insurance information was not provided during the vaccine encounter. This potential exposure misclassification is minimized in the self-controlled design in Phase 1; misclassification of exposure in Phase 2 would be expected to bias the results towards the null (CDC, 2023e). Furthermore, the presence of a claim for a filled prescription does not indicate that the medication was consumed or that it was taken as prescribed. Medications paid for out-of-pocket, as well as those not dispensed through a pharmacy, will not be observed in the claims data. Similarly, we may not have complete history of comorbidity or treatment for individuals due to switching in health plan insurer.

The study power may be limited by the short duration of accrual and a limited follow-up period, particularly during Phase 1. Because the COMIRNATY 2023-2024 Formula was approved in September 2023, the study may be underpowered to conduct comparisons at the interim report stage.

Lastly, in all observational studies, treatment is not randomly assigned, and there is potential for residual confounding by factors not captured or poorly measured in claims databases. As often used in pharmacoepidemiology, a 1-year covariate assessment period prior to cohort entry will be used to control for potential baseline confounding in Phase 2. Use of a longer covariate assessment period may increase the capture of chronic conditions. However, most individuals with a chronic condition are expected to interact with the healthcare system at least once per year, suggesting that a 1-year covariate assessment period may be sufficient for capturing chronic conditions. Nevertheless, those without a visit in the 1-year baseline period may be missed. Additionally, prior COVID-19 vaccination in the previous year is an important potential confounder, but it could not be included in the propensity score model in Phase 2 due to potential positivity violations. Individuals who received a COVID-19 vaccine in the 270 days prior to cohort entry date will be excluded from the study, so by design, COVID-19 vaccination in the previous year is not an informative variable, as it would only capture COVID-19 vaccination in the 365 days to 271 days prior to receipt of the COMIRNATY 2023-2024 Formula. Finally, receipt of other vaccinations at baseline besides seasonal influenza vaccines and RSV vaccines will not be included in the propensity score model, which may result in residual confounding. To minimize this potential bias, the most common baseline procedure codes will be examined to identify additional baseline vaccinations that may be potential confounders. Baseline vaccinations other than seasonal vaccination or RSV that are identified during this process will be considered for inclusion in the propensity score model.

A strength of the current study is its incorporation of a self-controlled design, which eliminates the concern of confounding by time-fixed characteristics that vary across individuals. Similarly, in Phase 2, careful PS matching of the COMIRNATY and comparator cohorts is expected to minimize residual confounding in the cohort analysis. Finally, capture

of current COVID-19 vaccines is likely better within the commercially insured population as compared to prior years, when there were more opportunities for individuals to receive a COVID-19 for free without utilizing their insurance (CDC, 2023e).

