## 9.2. Setting

The source population for this study will consist of all individuals with at least one medical or pharmacy claim from 11 September 2023 through 31 March 2024. The end date of 31 March 2024 was chosen based on the assumption that vaccine uptake will be similar to uptake during the 2022-2023 season. During the 2022-2023 COVID-19 season, the end of March reflected the time when uptake of the bivalent booster was no longer increasing (i.e., most individuals who received the bivalent booster dose had done so prior to March 2023), and COVID-19 cases declined substantially from their peak ([CDC, 2020](#)).

Trends in COVID-19 vaccine uptake will be monitored until 30 June 2024 using the Centers for Disease Control and Prevention's (CDC) Weekly COVID-19 Vaccination Dashboard ([CDC, 2023d](#)), which publishes estimates of the proportions of children aged 6 months through 17 years and adults 18 years and older who have received a COVID-19 vaccine each week during the 2023-2024 season. If in the final week of reported data for June 2024 these estimates show vaccine uptake in either children or adults that is 1% or greater than the respective estimates reported for the first week of April 2024 (i.e., an increasing trend in COVID-19 vaccine uptake from the first week of April 2024 to the last week of June 2024), then the Sponsor will extend the end date of the accrual period into October 2024, and the updated source population will be reflected in the final study report. This date reflects the latest accrual date that still allows for meeting of the current study milestones. This revision, if needed, will be communicated to the FDA as a protocol amendment.

Each study design will have its own inclusion and exclusion criteria, as listed below.

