#### **9.2.2.2. Exclusion Criteria**

Patients meeting any of the following criteria will not be included in Phase 2 of the study:

1. Are of unknown sex.
2. Have a missing month and year of birth.
3. Have received a COVID-19 vaccine in the 270 days prior to cohort entry date (as defined in Section 9.2.3).
4. Have received both the COMIRNATY 2023-2024 Formula and a COVID-19 vaccine other than the COMIRNATY 2023-2024 Formula on the cohort entry date (defined in Section 9.2.3).

In both phases of the study, when creating the analytic population for each specific safety outcome of interest, individuals will be excluded if they experienced that safety outcome during the portion of the baseline period designated as the clean period ([Section 9.2.4](#)).

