#### **Prior COVID-19 Vaccination – Descriptive only (not for inclusion in PS model)**

- Receipt of COVID-19 vaccine doses (any brand) prior to 2023-2024
  - Because COVID-19 vaccination in the 270 days prior to cohort entry is an exclusion criterion ([Section 9.2.2.2](#)), this variable will only capture COVID-19 vaccinations in the 365 days through 271 days prior to cohort entry
- Days from the most recent prior COVID-19 vaccine dose (any brand) to first vaccination with 2023-2024 formulations (for all Phase 1 individuals, as well as Phase 2 individuals receiving COMIRNATY or another 2023-2024 formulation)

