### **COVID-19 Vaccination – Descriptive only (not for inclusion in PS model)**

- Site of vaccination (e.g., outpatient, pharmacy)
- Source of vaccination information (e.g., CPT code, NDC)
- Number of doses prior to 2023-2024, by vaccine product
- Average number of days between doses of COMIRNATY 2023-2024 Formula, among those with multiple doses

Code lists for covariates are included in [Appendix IV](#).

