#### 9.7.2.4. Subgroup Analysis

If sample size permits, the main analysis will be restricted to the following subgroups:

- Individuals with concomitant administration of a non-COVID-19 vaccine (e.g., seasonal influenza, RSV) on cohort entry date; specific analyses will be performed among individuals receiving seasonal influenza vaccine and those receiving RSV vaccine
- Immunocompromised individuals
- Individuals with specific baseline comorbidities, such as a chronic lung, heart, kidney or liver condition; cancer; Down syndrome or other neurological or neurodevelopmental disorders; and blood disorders
- Individuals with prior SARS-CoV-2 infection
- Individuals with prior COVID-19 vaccination
- Pregnant women
- Individuals aged < 18 years
- Individuals aged  $\geq$  65 years

For the subgroup analysis, the propensity score will be included in the model as a covariate, given that some matched strata may be broken by restricting both the COMIRNATY 2023-2024 Formula cohort and the comparator cohort by the above attributes. As with the primary analysis, unconditional Poisson regression will be used, and the model will account for individuals who are included in both groups.

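### Prior COVID-19 vaccination is kept out of the Phase 2 propensity score on a positivity argument that the shared 270-day exclusion does not support, and the balance checks do not cover it

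*Protocol*

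**What the plan says.** Section 9.9 of the protocol makes three statements about this variable in the Phase 2 cohort study:

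- "prior COVID-19 vaccination in the previous year is an important potential confounder".
- "it could not be included in the propensity score model in Phase 2 due to potential positivity violations".
- By design, "COVID-19 vaccination in the previous year is not an informative variable", because the 270-day exclusion leaves only a narrow part of the baseline year.

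Section 9.3.3 lists the variable as descriptive only and explains that "this variable will only capture COVID-19 vaccinations in the 365 days through 271 days prior to cohort entry". The propensity score (PS) equation in Section 9.7.2.1 has no term for it.

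The exclusion itself is criterion 3 in Section 9.2.2.2: "Have received a COVID-19 vaccine in the 270 days prior to cohort entry date". It covers all Phase 2 patients, vaccinees and comparators alike. Section 9.7.2.4 lists "Individuals with prior COVID-19 vaccination" among the subgroups in which the main comparison is to be repeated, if sample size permits.

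**The concern.** Positivity fails by design when some covariate level can occur in only one exposure group. An exclusion applied identically to both groups removes the same people from each and does not have that effect. The second reason, that the variable is uninformative, sits badly beside the statement that it is an important potential confounder.

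The other safeguards do not cover the gap. Section 9.7.2.1 assesses standardized differences for covariates in the PS model, and Section 9.7.2.2 adds covariates to the Poisson model when those differences show imbalance. A variable outside the PS model does not enter that route, however unbalanced it is. A measured potential confounder could therefore remain uncontrolled in the primary Phase 2 rate ratios of a study that is a condition of authorization.

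**Working it through.** **1. The capture window.** The inputs are the 365-day baseline (Section 9.2.4) and the 270-day exclusion (Section 9.2.2.2). Days -365 to -271 make 365 - 271 + 1 = 95 days, or 95/365 = 26% of the baseline year. This reproduces the window in Section 9.3.3. In calendar time:

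| Cohort entry | Window captured |
|---|---|
| 11 Sep 2023 | 11 Sep 2022 to 14 Dec 2022 |
| 15 Oct 2023 | 15 Oct 2022 to 17 Jan 2023 |
| 31 Dec 2023 | 31 Dec 2022 to 4 Apr 2023 |
| 31 Mar 2024 | 1 Apr 2023 to 4 Jul 2023 |

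Section 7 dates the bivalent vaccines from August 2022, and Section 9.2 says that "most individuals who received the bivalent booster dose had done so prior to March 2023". The window lies inside that campaign for September and October entrants and after most of it for the latest entrants.

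**2. Positivity by design.** Let X = 1 if a dose falls in days -365 to -271.

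| Most recent dose before entry | COMIRNATY cohort | Comparator cohort |
|---|---|---|
| Within 270 days | excluded | excluded |
| 271 to 365 days (X = 1) | eligible | eligible |
| Earlier, or none (X = 0) | eligible | eligible |

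Both levels of X are allowed in both cohorts. The protocol itself foresees prior vaccinees among comparators. Section 9.3.3 describes days since the last dose for Phase 2 recipients of another 2023-2024 formulation, who are comparators under Section 9.7.2.3. The subgroup in Section 9.7.2.4 also restricts both cohorts to prior vaccinees.

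**3. Positivity in numbers.** The protocol gives no prevalences, so these are assumptions: p1 = 0.2 to 0.6 of vaccinees and p0 = 0.01 to 0.10 of comparators have X = 1, with k = 1 to 10 candidate comparators per vaccinee. Five (p1, p0) pairs were each run at k = 1, 5 and 10.

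- P(T=1|X=1) = p1/(p1 + k·p0). Lowest: 0.3/(0.3 + 10 × 0.1) = 0.23. Highest: 0.5/(0.5 + 1 × 0.02) = 0.96.
- P(T=1|X=0) = (1 - p1)/((1 - p1) + k(1 - p0)). Lowest: 0.4/(0.4 + 10 × 0.95) = 0.04. Highest: 0.8/(0.8 + 1 × 0.99) = 0.45.

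All lie strictly between 0 and 1. The supply of comparators with X = 1 per vaccinee with X = 1, k·p0/p1, runs from 0.02/0.5 = 0.04 to 10 × 0.1/0.3 = 3.33. Overlap exists by design, but it may be thin.

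**4. Possible imbalance.** The standardized difference is (p1 - p0)/√{[p1(1 - p1) + p0(1 - p0)]/2}. For 0.3 against 0.1 it is 0.2/0.387 = 0.52; for 0.6 against 0.05 it is 0.55/0.379 = 1.45. The protocol's limit is 0.1. These are values before matching on anything else.

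**5. Possible bias.** At a true rate ratio of 1, the observed ratio is [1 + p1(R - 1)]/[1 + p0(R - 1)], where R is the assumed outcome rate ratio for X = 1 against X = 0.

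| p1, p0 | R = 0.5 | R = 0.8 | R = 1.25 | R = 2 |
|---|---|---|---|---|
| 0.3, 0.10 | 0.895 | 0.959 | 1.049 | 1.182 |
| 0.5, 0.10 | 0.789 | 0.918 | 1.098 | 1.364 |
| 0.6, 0.05 | 0.718 | 0.889 | 1.136 | 1.524 |

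The range is 0.72 to 1.52. The direction depends on R, which the protocol does not give.

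**The case against.** The protocol discloses the omission as a limitation and words it cautiously: a potential confounder and potential violations. Several further points stand.

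- **Sparse cells.** Matching is within age group and 14-day period, and some strata may hold few or no comparators with X = 1. A reader might infer that no positivity problem can arise at all. The documents support only the narrower statement that the exclusion does not create one. The prior-vaccination subgroup does not prove adequate overlap either, since it is conditional on sample size.
- **Late entrants.** For entry near 31 March 2024 the claim of little information is fair.
- **A coarse measure.** The window slides with entry date. A dose on 1 October 2022 counts for entry on 11 September 2023 (345 days) but not on 15 October 2023 (379 days).
- **Proxies.** Influenza and RSV vaccination, utilization and prior infection are in the PS, and frequent baseline procedure codes are screened. These may absorb part of the confounding. The self-controlled analysis and the comparison with recipients of other 2023-2024 COVID-19 vaccines offer partial cross-checks.
- **Longer history.** A reader might infer that all claims since December 2020 would settle the matter, especially as Section 9.3.3 also lists "Number of doses prior to 2023-2024, by vaccine product". That item is descriptive and says nothing about positivity. Section 9.9 acknowledges that earlier doses could be had free without using insurance, only 365 days of enrolment are required, and Section 9.6 ties a single extract per report to the baseline period.

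None of this repairs the stated reason. Sparse cells are a matter to check, and the protocol cites no such check. A coarse indicator is still informative for autumn entrants.

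**Conclusion.** The concern holds in this form. The 270-day exclusion creates no structural positivity violation, and the variable is not uninformative for autumn 2023 entrants, although it says little for the latest ones. As written, the plan leaves a measured potential confounder outside both the PS and the balance check that would trigger adjustment.

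The size and direction of the resulting bias are unknown. The range of 0.72 to 1.52 rests on assumed prevalences and outcome ratios and makes no allowance for the covariates already matched on. It shows that the omission could matter, not that it does. A reader might infer that every Phase 2 rate ratio is biased toward safety; the documents contain nothing that fixes the direction or shows that each outcome is affected.

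**What to change.** 1. Add the 271-365-day indicator, already defined in Section 9.3.3, to the PS model, with the interaction with calendar month that Section 9.7.2.1 permits. The interaction lets its weight differ between early and late entrants.
2. Report its standardized difference after matching and its cell counts by cohort, including within age-by-14-day strata.
3. If sparse cells prevent its use in the PS, include it in the outcome model when the standardized difference exceeds 0.1.
4. In Section 9.9, delete or correct the positivity and uninformative-variable sentences. If positivity is still claimed, support it with the cell counts.
5. Where data allow, use a longer lookback as a sensitivity analysis. Section 9.2.4 permits other windows for specific covariates. State the under-capture of earlier free doses and the uneven enrolment.

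Cost: items 1 to 4 use data within the existing 365-day baseline, so they need one main term and its interaction, and a rerun of the match and the analyses that follow. With version 3.0 dated 18 March 2026 and the final report planned for 30 April 2026, the time is short. Some vaccinees may go unmatched, probably few unless comparators with a dose in the window are scarce. The indicator will still miss doses given more than a year before entry. Item 5 may need a further extract.

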### **9.10. Other Aspects**

Not applicable.

## **10. PROTECTION OF HUMAN PARTICIPANTS**

### **10.1. Patient Information**

This study involves data that exist in deidentified/anonymized structured format and contains no patient personal information.

### **10.2. Patient Consent**

As this study involves deidentified/anonymized structured data, which according to applicable legal requirements do not contain data subject to privacy laws, obtaining informed consent from patients by Pfizer is not required.

### **10.3. Institutional Review Board (IRB)/Ethics Committee (EC)**

Optum will prepare and submit the appropriate documents to a central IRB for Optum's conduct of the project. Optum will communicate directly with the IRB to address any questions and/or provide any additional information in connection with the review. Pfizer shall provide any necessary assistance or documents required for the submission to the IRB. Approval from an IRB for this project is not guaranteed. This project will be undertaken only after the study combined protocol/SAP has been approved by the IRB or granted an Exemption Determination Letter from the IRB. The IRB will monitor the study for the life of the project and may require formal re-review and approval on an annual basis. Changes to the project may also require re-review and approval by the IRB.

There must be prospective approval of the study protocol/SAP, protocol/SAP amendments, and other relevant documents (e.g., informed consent forms if applicable) from the relevant IRBs or ECs. All correspondence with the IRB/EC must be retained. Copies of IRB/EC approvals must be forwarded to Pfizer.

### **10.4. Ethical Conduct of the Study**

The study will be conducted in accordance with legal and regulatory requirements, as well as with scientific purpose, value, and rigor and follow generally accepted research practices described in the following guidance documents:

- Guidelines for GPP. Public Policy Committee, International Society of Pharmacoepidemiology. Pharmacoepidemiology and Drug Safety 2015; 25:2-10;
- International Ethical Guidelines for Epidemiological Studies issued by the Council for International Organizations of Medical Sciences (CIOMS);

- EMA European Network of Centres for Pharmacoepidemiology and Pharmacovigilance (ENCePP) Guide on Methodological Standards in Pharmacoepidemiology;
- FDA Guidance for Industry: Good Pharmacovigilance Practices and Pharmacoepidemiologic Assessment; and
- FDA Guidance for Industry and FDA Staff: Best Practices for Conducting and Reporting Pharmacoepidemiologic Safety Studies Using Electronic Healthcare Data.

## **11. MANAGEMENT AND REPORTING OF ADVERSE EVENTS/ADVERSE REACTIONS**

This study involves data that exist as structured data by the time of study start. In these data sources, it is not possible to link (i.e., identify a potential association between) a particular product and medical event for any individual. Thus, the minimum criteria for reporting an adverse event (AE) (i.e., identifiable patient, identifiable reporter, a suspect product, and event) cannot be met.

